2.1.1 Sample size calculation for the CGM and meal test subgroup

The CGM and meal test subgroup is included in the trial in order to compare additional assessments for evaluation of postprandial and overall glucose regulation between the treatment arms. As this additional assessment is exploratory in nature, this subgroup is not strictly powered to demonstrate a statistical significant difference between treatment arms in any particular endpoint. Fifty (50) Subjects per treatment arm have been chosen as this number is considered enough to provide sufficient information for evaluation in this exploratory analysis, and as this is a similar number to what have been included in previous trials using CGM subgroups.

2.2 Definition of analysis sets

The following analysis sets are defined in accordance with the ICH-E9 guidance¹:

- FAS includes all randomised Subjects. In exceptional cases randomised Subjects may be excluded from the FAS. In such cases the reason for exclusion will be justified and documented. Subjects in the FAS will contribute to the evaluation “as randomised”
- Per Protocol (PP) Analysis Set includes all Subjects in the full analysis set that comply with inclusion and exclusion criteria. Subjects in the PP set will contribute to the evaluation “as treated”
- SAS includes all Subjects receiving at least one dose of the investigational product or its comparator. Subjects in the safety set will contribute to the evaluation “as treated”

Randomised Subjects who are lost to follow up, and where no exposure information of the investigational product or its comparator is available after randomisation, will be handled as unexposed.

Before data are released for statistical review after 26 weeks, a blinded review of all data will take place to identify protocol deviations that may potentially affect the results. Furthermore, extreme values and outliers will be identified by the statistician during programming and data review, according to ICH-E9¹.

If any Subjects or observations are excluded, the reasons for their exclusion must be documented and signed by those responsible before database lock. The Subjects and observations excluded from analysis sets, and the reason for this, will be described in the clinical trial report.

2.3 Primary endpoint

The primary endpoint to address all three confirmatory objectives is:

Change from baseline in HbA_{1c} 26 weeks after randomisation

Primary analysis

- 1) The primary estimand will be addressed by the below primary analysis on all Subjects included in FAS and using the in trial observation period. Note that if Subjects withdraw consent to contribute additional information or are completely lost to follow-up, actual missing data will occur. The primary analysis will be implemented as a statistical model using multiple imputation where the Subjects without any available HbA_{1c} measurements at scheduled visits will have their change from baseline HbA_{1c} value(s) imputed from the available information from the treatment the Subject has been randomised to. Note that this resembles in essence a mixed model of repeated measurements analysis. Subjects without post-randomisation measurements contribute to the analysis, as the missing values will be imputed. The analysis will be implemented as follows:

- In the first step, intermittent missing values are imputed using a Markov Chain Monte Carlo (MCMC) method, in order to obtain a monotone missing data pattern. This imputation is done for each group separately and 100 copies of the dataset will be generated.
- In the second step, for each of the 100 copies of the dataset, an analysis of variance model with region and strata as factors and baseline HbA_{1c} as covariate is fitted to the change in HbA_{1c} from baseline to week 12 for each treatment group separately. The estimated parameters, and their variances, from these models are used to impute missing values at week 12 for Subjects in each treatment group, based on region, strata, and baseline HbA_{1c}.
- In the third step, for each of the 100 copies of the dataset, missing values at week 26 are imputed in the same way as for week 12. The imputations are based on an analysis of variance model with region and strata as factors and baseline HbA_{1c} and HbA_{1c} at week 12 as covariates.
- For each of the complete data sets, the change from baseline to week 26 is analysed using an analysis of variance model with treatment, region and strata as factors, and baseline HbA_{1c} as a covariate.
- The estimates and standard deviations for the 100 data sets are pooled to one estimate and associated standard deviation using Rubin's formula:

$$m_{MI} = \frac{1}{100} \sum_{i=1}^{100} m_i, \quad SD_{MI} = \sqrt{\frac{1}{100} \sum_{i=1}^{100} SD_i^2 + \left(1 + \frac{1}{100}\right) \left(\frac{1}{100-1}\right) \sum_{i=1}^{100} (m_i - m_{MI})^2},$$

- where m_i and SD_i are the estimated means and standard deviations for the 100 copies of the dataset, and m_{MI} and SD_{MI} are the pooled estimates.
- From m_{MI} and SD_{MI} , the 95% confidence interval for the treatment differences is calculated.

All three objectives will be addressed by treatment differences and associated 95% confidence interval obtained from the same primary statistical model described above.

Non-inferiority of meal-time fast-acting insulin aspart will be considered confirmed if the upper boundary of the two-sided 95% confidence interval is below or equal to 0.4% or equivalent if the p-value for the one-sided test of

$$H_0: D > 0.4\% \quad \text{against} \quad H_A: D \leq 0.4\%,$$

is less than or equal to 2.5%, where D is the mean treatment difference (meal-time fast-acting insulin aspart minus meal-time NovoRapid®).

If the primary objective is confirmed, the effect of treatment with post-meal fast-acting insulin aspart in terms of glycaemic control is to be investigated by showing that post-meal fast-acting insulin aspart is non-inferior to NovoRapid® both in combination with insulin degludec in terms of glucose lowering effect, as assessed by change from baseline in HbA_{1c} 26 weeks after randomisation. This will be determined in the same way as above where treatment difference is set to (post-meal fast-acting insulin aspart minus meal-time NovoRapid®).

Finally, if both the primary and the first secondary confirmatory hypotheses are fulfilled, the superiority of the meal-time fast-acting insulin aspart as compared to meal-time NovoRapid® will be tested in terms of glycaemic control. This will be assessed by comparing the upper limit of the 95% CI from the primary analysis to 0. If the upper 95% CI is below 0 then superiority will be confirmed.

Sensitivity analyses for the primary analysis addressing the primary estimand

- 2) First, the primary analysis in 1) will be repeated, but excluding all factors except treatment from the multiple imputation and analysis of variance models while still including baseline HbA_{1c} as a covariate. This analysis will explore the influence of the different factors. The analysis will use the in-trial observation period.
- 3) The primary analysis approach chosen for this trial relies on the assumption that missing data is missing at random (MAR). This assumption implies that the HbA_{1c} for Subjects leaving the trial, after their withdrawal, develops in a similar way as the HbA_{1c} for similar Subjects that remain in the trial (not necessarily on treatment) and had similar development of HbA_{1c} before withdrawal. The MAR assumption may be questionable for Subjects withdrawing at own will or at the discretion of the Investigator. Therefore the statistical model using multiple imputation will be repeated with the following alterations:
 - a. Imputation will be done from the treatment arm that the Subject was randomised to and a value of 0.4% (the non-inferiority margin) is added to the change in HbA_{1c} at 26 weeks for Subjects, on either of the fast-acting insulin aspart arms, with an imputed value at week 26². This will serve as a sensitivity analyses for the non-inferiority analyses. The analysis will use the in trial observation period.
 - b. Imputation will be done from the comparator arm (NovoRapid®). This will serve as a sensitivity analysis for the superiority analysis. The imputation will be done conditional on observed information for Subjects on fast-acting insulin aspart without a measurement at week 26 such that the treatment effect diminishes gradually (copy reference/conditional imputation). It does not rely on the MAR assumption, but assumes that Subjects on fast-acting insulin aspart without a measurement at week 26 switch to NovoRapid®. The analysis will use the in trial observation period.

- c. Imputation will be done from the comparator arm (NovoRapid®). This will serve as a supplementary sensitivity analysis for the superiority analysis. The imputation will be done with no regard to observed information for Subjects on fast-acting insulin aspart without a measurement at week 26 such that the treatment effect diminishes immediately (jump to reference/unconditional imputation). It does not rely on the MAR assumption, but assumes that Subjects on fast-acting insulin aspart without a measurement at week 26 switch to NovoRapid®. The analysis will use the in trial observation period.
- d. A tipping point analysis based on a statistical model using multiple imputations similar to 1), using the in trial observation period, will be made. In this analysis, observations for Subjects without a measurement are imputed based on the treatment arm they were randomised to and Subjects without a measurement in the fast-acting insulin aspart group under investigation are given a penalty. Specifically, for treatment differences involving the meal-time fast-acting insulin aspart group, only Subjects in this group are given a penalty, and vice versa for treatment differences involving the postmeal fast-acting insulin aspart group. This is done to investigate the robustness of the conclusion in the primary analysis with respect to the MAR assumption and mimics a scenario where the HbA_{1c} of the Subjects without a measurement in the fast-acting insulin aspart group under investigation evolve less favourably than predicted. As a first step imputations will be done without penalty assuming MAR in the treatment group. Second, a penalty will be added to the imputed values for week 26 in the fast-acting insulin aspart group under investigation. This is done repeatedly, gradually increasing the penalty until the conclusions of the primary analysis no longer hold. The specific value of the penalty that changes the conclusion will be used to evaluate the robustness of the conclusion of the primary analysis.

Analyses addressing the secondary estimand

- 4) The secondary estimand will be analysed using the same statistical model using multiple imputation as the primary analysis in 1) except using the on treatment observation period. The analysis will use the FAS.
- 5) A tipping point analysis based on a statistical model using multiple imputation, similar to sensitivity analysis 3)-d except using the on treatment observation period.
- 6) A tipping point analysis based on a statistical model using multiple imputation, similar to 5) but with the modification that Subjects without a measurement that discontinued treatment due to non-eligibility (Subjects discontinuing fast-acting insulin aspart/NovoRapid® prematurely due to criteria 1, 2, 3, and 4 of Section 6.6 in the trial protocol) in the fast-acting insulin aspart

group under investigation will not have a penalty added to the imputed values. These analyses are motivated by the fact that data from Subjects prematurely discontinuing fast-acting insulin aspart/NovoRapid® due to non-eligibility can reasonably be assumed to be missing completely at random. The analysis will use the on treatment observation period.

- 7) The same statistical model using multiple imputation as the primary analysis in 4), but using the PP analysis set and analysed using the on treatment observation period. This analysis will investigate the situation that Subjects deviate from the ideal treatment during the on treatment observation period and will serve as a sensitivity analysis for the non-inferiority analysis.

2.4 Secondary endpoints

2.4.1 Supportive secondary endpoints

For all supportive secondary endpoints, meal-time fast-acting insulin aspart will be compared to meal-time NovoRapid®, and post-meal fast-acting insulin aspart will be compared to meal-time NovoRapid®. Change from baseline refers to the change from randomisation to 26 weeks after randomisation.

2.4.1.1 Efficacy endpoints

All endpoints except insulin dose in this section will be assessed using the FAS and the in trial observation period and repeated using the on treatment observation period. Insulin dose will only be presented using the on treatment observation period.

The following endpoints will be assessed 26 weeks after randomisation:

Change from baseline in 8-point profiles.

PPG increments based on the 8-point profiles will be derived separately for plasma glucose (PG) measurements made 1 hour after the meal. In the following section this distinction will be considered implicit and without further explanation. PPG will be recorded by the Subject as part of two 8-point profiles prior to the visits. PPG increment for each meal (breakfast, lunch, main evening meal) will be derived from the 8-point profile as the difference between PPG values and the PG value before meal in each separate profile. The mean of the derived increments will then be calculated separately for each meal. Mean PPG increment over all meals will be derived as the mean of all corresponding mean meal increments.

- Change from baseline in mean PPG and PPG increment over all three meals

Mean PPG and PPG increment will be analysed separately using a model similar to 1), except with the corresponding baseline value as covariate.

- Change from baseline in individual meal (breakfast, lunch and main evening meal)
PPG and PPG increment from 8-point profile

PPG and PPG increment endpoints for the individual meals (breakfast, lunch, main evening meal) will be analysed separately using a model similar to 1) except with the corresponding baseline value as covariate.

- Change from baseline in mean of the 8-point profile

The mean of the 8-point profile is defined as the area under the profile divided by the measurement time, and is calculated using the trapezoidal method. Mean of the 8-point profile will be analysed using a model similar to 1) except with the corresponding baseline value as covariate.

- Fluctuation in 8-point profile

The fluctuation in the 8-point profile is defined as

$$\frac{1}{T} \int_0^T |PG(t) - \bar{PG}| dt,$$

where T , $PG(t)$ and \bar{PG} denotes the length of the profile, the PG value at time t and the mean of the profile, respectively. Fluctuation in the 8-point profile will be logarithmically transformed and analysed in the same way as mean of the profile is analysed except with the corresponding log-transformed baseline values as covariate. Estimated treatment means and the estimated treatment difference with corresponding 95% CI will be back-transformed to the original scale, resulting in estimated geometric means, a treatment ratio and a 95% CI for the treatment ratio.

- Change from baseline in FPG

Change from baseline in FPG will be analysed using a model similar to 1) except with baseline FPG as covariate.

- Change from baseline in 1,5-anhydroglucitol

Change from baseline in 1,5-anhydroglucitol will be using a model similar to 1) except with baseline 1,5-anhydroglucitol as covariate.

- Percentage of Subjects reaching HbA_{1c} target (HbA_{1c} < 7.5%) according to ISPAD guidelines³

This dichotomous (responder/non-responder) endpoint will be defined based on whether a Subject has met the ISPAD HbA_{1c} target (HbA_{1c} < 7.5%) 26 weeks after randomisation.

This responder endpoint will be analysed based on a logistic regression model using treatment, region and strata as factors, and baseline HbA_{1c} as covariate. In the in trial

observation period analysis, Subjects withdrawn from trial are included as non-responders. In the on treatment observation period analysis, both Subjects who prematurely discontinue fast-acting insulin aspart/NovoRapid® or withdraw from trial are included as non-responders. Subjects without HbA_{1c} at week 26 will be treated as non-responders for both the in trial and on treatment observation period analyses.

- Percentage of Subjects reaching HbA_{1c} target (HbA_{1c} < 7.5%) according to ISPAD guidelines, without severe hypoglycaemia³.
This dichotomous (responder/non-responder) endpoint will be defined based on whether a Subject has met the ISPAD HbA_{1c} target (HbA_{1c} < 7.5%) 26 weeks after randomisation without treatment emergent severe hypoglycaemic episodes³.
This responder endpoint will be analysed based on a logistic regression model using treatment, region and strata as factors, and baseline HbA_{1c} as covariate. In the in trial observation period analysis, Subjects withdrawn from trial are included as non-responders. In the on treatment observation period analysis, both Subjects who prematurely discontinue fast-acting insulin aspart/NovoRapid® or withdraw from trial are included as non-responders. Subjects without HbA_{1c} at week 26, will be treated as non-responders for both the in trial and on treatment observation period analyses.
- Insulin dose (total basal, total bolus and individual meals insulin dose).
Bolus insulin doses will be recorded together with time of administration. The insulin doses will be summarised descriptively by treatment week according to regimen, both by meal type and as total daily dose in units and units/kg (total daily and separately for each meal-time dose). Insulin doses will be summarised using the on treatment observation period and using the SAS.

Supportive secondary CGM related efficacy endpoints

The following endpoints will be assessed 26 weeks after randomisation:

- Change from baseline of time spent in low interstitial glucose (IG) (IG ≤ 3.9 mmol/L [70 mg/dL])

The time spent in low IG is defined for each Subject at each CGM period as the accumulated time in hours spent below or equal to 3.9 mmol/L from the first valid sensor value divided by the actual duration of the entire profile. To report the endpoint in minutes per 24 hours the ratio is multiplied by 1440. The endpoint will be analysed using an analysis of variance model including treatment, region and strata as factors and the baseline value of time in low IG as covariate.

- Incidence of episodes and percentage of time spent with IG ≤ 2.5, 3.0, 3.9 mmol/l [45, 54, 70 mg/dL]) and IG > 10.0, 12.0, 13.9 mmol/l [180, 216, 250 mg/dL])

- Percentage of time spent within IG target range 4.0-10.0 mmol/L (71-180 mg/dL)
- Change from baseline in mean of the IG profile

The mean of the IG profile will be defined as:

$$\bar{IG} = \frac{1}{T} \int_0^T IG(t) dt,$$

where T is the time length of the profile and $IG(t)$ is the IG value at time t . (Here $t=0$ represents the time point for the start of the profile.) This mean will be calculated by means of the linear trapezoidal technique.

- Variation in the IG profile

The variation in the IG profile will be presented by the fluctuation, which is defined as:

$$\frac{1}{T} \int_0^T |IG(t) - \bar{IG}| dt,$$

where T is the time length of the profile, $IG(t)$ is the IG value at time t , and \bar{IG} is the mean of the IG profile as defined above. (Again, here $t=0$ represents the time point for the start of the profile.) The integral will be calculated by the linear trapezoidal technique. The coefficient of variation (CV%) will also be calculated to describe the IG variation.

IG measurements during meal test will be excluded.

All CGM endpoints will be summarised descriptively by treatment.

Supportive secondary CGM and meal-characteristics efficacy endpoints

The following endpoints will be assessed 26 weeks after randomisation:

Change from baseline in meal characteristics of IG profile (4 hours after start of each meal), measured as:

- Change from baseline in mean IG increment (0-1 hours and 0-2 hours after start of the meal)

The mean IG (meal) increment will be defined as the mean across main meals of the prandial increments, i.e. the difference between IG 1 hours (or 2 hours, respectively) after the meal and IG before the meal

- Change from baseline in mean IG peak after start of meal

The mean IG peak after start of meal will be derived as mean across main meals of the IG maximum values within 4 hours after start of the meal.

- Change from baseline in mean time to the IG peak after meal

The mean time to the IG peak after meal is derived as the mean time to the IG peak across main meals.

These endpoints will also be derived for each main meal separately (breakfast, lunch and main evening meal). IG measurements during meal test will be excluded. The endpoints will be analysed separately, using an analysis of variance model including treatment, region and strata as factors and the corresponding baseline value as covariate.

All CGM endpoints will be summarised descriptively by treatment.

Supportive secondary meal test related efficacy endpoints

The following endpoints will be assessed 26 weeks after randomisation:

- Change from baseline in 30-min PPG and PPG increment
- Change from baseline in 1-hour PPG and PPG increment
- Change from baseline in 2-hour PPG and PPG increment

Laboratory measured plasma glucose from the meal test will be analysed for 30-min, 1-hour and 2-hour PPG separately. The corresponding PPG increments will be derived separately using each PPG measurement minus the pre-prandial PG.

Change from baseline 26 weeks after randomisation in PPG and PPG increment endpoints will be analysed separately using an analysis of variance model including treatment, region and strata as factors and the corresponding baseline value as covariate.

All PPG endpoints will be summarised descriptively by treatment.

Supportive secondary CGM and meal test related efficacy endpoints

Endpoints listed below will be assessed during meal test and based on CGM measurements.

The following endpoints will be assessed 26 weeks after randomisation:

- Change from baseline in $AUC_{IG,0-15min}$
- Change from baseline in $AUC_{IG,0-30min}$
- Change from baseline in $AUC_{IG,0-1h}$
- Change from baseline in $AUC_{IG,0-2h}$

- Change from baseline in $AUC_{IG,0-4h}$
- Change from baseline in time to the IG peak after start of meal
- Change from baseline in IG peak after start of meal

$AUC_{IG,0-15\text{ min}}$, $AUC_{IG,0-30\text{ min}}$, $AUC_{IG,0-1\text{h}}$, $AUC_{IG,0-2\text{h}}$, and $AUC_{IG,0-4\text{h}}$ will be calculated as the area under the IG curve using the trapezoidal method and weighted by duration. The endpoint will also be calculated as increment where an average of the IG concentrations immediately before the meal is subtracted from the weighted AUC. Each endpoint will be analysed using an analysis of variance model including treatment, region and strata as factors and the corresponding baseline value as covariate.

IG peak and time to IG peak 26 weeks after randomisation will be compared separately between treatments using an analysis of variance model including treatment, region and strata as factors and with the corresponding baseline value as covariate.

All CGM endpoints will be summarised descriptively by treatment.

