6.7 Withdrawal from trial

The Subject may withdraw at will at any time either by the Subject or by the Subject's LAR(s). The Subject's request to discontinue must always be respected.

If the Subject considers withdrawing consent the Investigator must underline to the Subject the importance of continuing in the trial despite trial product discontinuation. If the Subject agrees to discontinue trial product but to stay in the trial, procedures similar to those described in section [8.2](#) must be followed.

If a Subject decides to withdraw informed consent the Subject should be encouraged to undergo procedures as described in section [8.3](#)

A Subject included in the trial in violation of the inclusion and/or exclusion criteria and/or randomised in violation of the randomisation criteria must discontinue treatment with trial product, but will not be withdrawn from the trial and will be followed as described in section [8.2](#)

A subject will be considered lost to follow-up if he/she repeatedly fails to attend the scheduled visits and the site staff is unable to establish contact with the subject.

The following actions must be taken in relation to a subject who fails to attend the site for a required visit:

- The site must attempt to contact the subject and reschedule the missed visit as soon as possible
- The site must re-train the subject in the importance of maintaining the scheduled visits
- In cases in which the subject is deemed lost to follow-up the investigator must make every effort to regain contact with the subject (e.g. telephone calls to friends or family members, e-mails or certified letter to the subject as applicable). These contact attempts should be documented in the subject's medical records. Should the subject continue to be unreachable, only then will he/she be considered to have withdrawn from the trial with the primary reason being "lost to follow-up"

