8.1.10 Follow-up periods

Follow-up visit 1 (FU1) (Visit 41) is a site visit and must take place 7-12 days after the actual date of an End of Treatment. Follow-up visit 2 (FU2) (Phone Contact 42) must take place 30-35 days after the End of Treatment.

8.1.10.1 Follow-up Visit 1

After the first follow-up period (7 days) the following data will be collected:

- AEs
- Concomitant medication
- Current diabetes medication
- Hypoglycaemic episodes

- Hyperglycaemic episodes
- Injection site reactions

The diary, handed out at the End of Treatment visit for collection of hypoglycaemic and hyperglycaemic episodes, should be returned by the Subject at this visit.

8.1.10.2 Follow-up Visit 2

After the last follow-up period (30 days) the following data will be collected during the phone contact:

- AEs
- Concomitant medication
- Current diabetes medication

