1.2 Scope of the statistical analysis plan

This statistical analysis plan (SAP) is based on the protocol *Efficacy and Safety of Faster-acting insulin aspart compared to NovoRapid® both in Combination with Insulin Degludec in Children and Adolescents with Type 1 Diabetes*, version 5.0 (dated 16 January 2017). The statistical analyses and derivations of endpoints presented in this SAP are almost identical to those described in the protocol. It contains minor clarifications for derivations, calculation of endpoints and analyses as well as a few additions.

The changes to the statistical considerations proposed in this SAP and the reasons for the changes are described in section [3](#) and will be reported in the clinical trial report (CTR).

2 Statistical considerations

General considerations

In general, for endpoints evaluated as a change from baseline and/or where a baseline adjustment is made, baseline is defined as information collected at the randomisation visit (Visit 14). In case a measurement is not available at the randomisation visit, the most recent measurement prior to the randomisation visit will be used as baseline.

Two observation periods are defined, “in trial” and “on treatment”, and it will be specified which period each analysis will use.

- In trial: the observation period from date of randomisation and until last trial -related Subject-site contact. The in trial observation period includes data collected after treatment discontinuation.
- On treatment: the observation period from date of first dose of randomised NovoRapid®/fast-acting insulin aspart and no later than 7 days after the day of last dose of NovoRapid®/fast-acting insulin aspart. The on treatment observation period includes data collected up to and including 7 days after treatment discontinuation.

All primary and secondary efficacy endpoints will be summarised and analysed using the full analysis set (FAS), unless otherwise stated. Safety endpoints will be summarised using the safety analysis set (SAS) and analysed using the FAS, unless otherwise stated.

Presentation of results from a statistical analysis will include the estimated mean treatment effects (LSMeans) for change from baseline, if applicable. Estimated mean treatment differences (or ratios) will be presented together with two-sided 95% confidence intervals for all endpoints analysed statistically.

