Subjects that prematurely discontinue from treatment or withdraw from trial will attend end of treatment visit called Visit 40A. Data collected at this visit will be reallocated to the next scheduled visit where the given assessment is planned. As a general rule, all observed values from randomised Subjects will be used in all statistical analyses, but in case two different values are associated to the same visit in time, the use of a given value will depend on the estimand of interest. For the primary estimand the reallocated on treatment value will not be used and for the secondary estimand the reallocated on treatment value will be used.

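### The withdrawal rule in both HbA1c responder endpoints has no time limit, so read literally it can score a measured week-26 responder as a failure

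*SAP*

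**What the plan says.** SAP 2.4.1.1 has two responder endpoints: reaching the HbA1c target, and reaching it without severe hypoglycaemia. The first is defined by whether a subject "has met the ISPAD HbA_{1c} target (HbA_{1c} < 7.5%) 26 weeks after randomisation"; the second adds the absence of treatment emergent severe episodes. The scoring rules are the same for both:

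- In trial analysis: "Subjects withdrawn from trial are included as non-responders".
- On treatment analysis: subjects who stop randomised bolus product early "or withdraw from trial are included as non-responders".
- Separately, subjects with no week-26 HbA1c "will be treated as non-responders for both the in trial and on treatment observation period analyses".

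Three other places bear on how the withdrawal clause is read:

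- Protocol 8.1.10 continues the trial beyond week 26: "Follow-up visit 2 (FU2) (Phone Contact 42) must take place 30-35 days after the End of Treatment". A site visit comes before it, at 7 to 12 days.
- Protocol 6.7 says of a subject who stays unreachable after documented contact attempts that "only then will he/she be considered to have withdrawn from the trial", with loss to follow-up as the reason. It also allows withdrawal at any time.
- SAP section 2, under visit reallocation, sets as a general rule that "all observed values from randomised Subjects will be used in all statistical analyses". The exception concerns two values that compete for the same visit.

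**The concern.** The endpoint asks a question about week 26, but the withdrawal clause refers to a status that can change up to about five weeks later. Take a subject who completes treatment, has HbA1c 7.0% at Visit 40, and then withdraws consent or cannot be reached during follow-up. Trial status is now withdrawn, so the clause as written makes this subject a failure in both analyses. The primary analysis in SAP 2.3 imputes only missing values and would use the same 7.0% as observed.

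Two things are at stake. The responder percentages can be slightly understated, and the arm comparison can pick up losses that say nothing about glycaemic control at week 26. Also, two programmers working from this text could score the same subject differently, one following the specific clause and the other the week-26 definition and the general rule.

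**Working it through.** **Plan's own figures.** The documents give no power, response rate or sample size for the responder endpoints. The figures in SAP 2.1 concern mean HbA1c change, and they reproduce. With 250 per group and SD 1.3, the standard error is 1.3 × √(2/250) = 0.1163. A margin of 0.4 with true difference 0 gives 93.0% power (stated: more than 93%). A difference of 0.05 gives 85.2% (stated: 85%). The point here changes neither, because the primary endpoint uses the observed week-26 value.

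**Reading the rules together.**

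1. The endpoint's time point is week 26 (SAP 2.4.1.1).
2. The withdrawal clause carries no date in either endpoint or either analysis.
3. The in trial period runs to the last subject-site contact (SAP section 2), so it includes follow-up after Visit 40.
4. Loss to follow-up counts as withdrawal, with no week-26 limit (Protocol 6.7).
5. From 2 to 4, a loss after Visit 40 meets the literal condition for non-response.
6. From 1 and the general rule on observed values, the Visit 40 measurement should decide the score.

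Steps 5 and 6 disagree, and no passage says which takes precedence.

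**What else the clause does.** SAP section 2 moves Visit 40A data to the next scheduled visit at which the assessment is planned. A subject who withdraws at, say, week 15 can therefore carry an HbA1c at week 26. The missing-value rule would not clearly catch that subject; the withdrawal clause does. The clause therefore has a proper use before week 26.

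**Number affected.**

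| Input | Value | Source |
|---|---|---|
| Subjects per arm | 250 | SAP 2.1 |
| Withdrawal, ceiling | 5% | SAP 2.1 (expected to be less) |
| Treatment period | 26 × 7 = 182 days | SAP 1.1 |
| Follow-up | 30 days (35 at the latest) | Protocol 8.1.10 |
| Timing of withdrawals | even over the period | assumption |
| Responder rate among those lost | 30% to 60% | assumption |

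- Withdrawals per arm at the ceiling: 250 × 0.05 = 12.5.
- Share after week 26: 30/(182 + 30) = 0.142.
- Subjects affected per arm: 12.5 × 0.142 = 1.8.
- Responders rescored per arm: 1.77 × 0.30 = 0.53 to 1.77 × 0.60 = 1.06.
- In percentage points: 0.53/250 = 0.21 to 1.06/250 = 0.42.

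With 35 days of follow-up the share is 35/217 = 0.161 and the range is 0.24 to 0.48 points. With 2.5% withdrawal and 30 days it is 0.11 to 0.21 points. The extreme bound puts all 5% after Visit 40: 12.5 × 0.30 = 3.75 to 12.5 × 0.60 = 7.5 responders per arm, or 1.5 to 3.0 points.

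**The case against.** The strongest reply is that the plan never says a measured week-26 value is replaced. The endpoint is defined at week 26, its list is headed as assessed at week 26, and observed values are to be used. The withdrawal procedure in Protocol 8.3 also fits someone who leaves before Visit 40: it asks sites to attempt Visit 40-type procedures and to register a treatment discontinuation, whereas a subject who reaches End of Treatment gets a completion session (Protocol 8.1.9). Loss to follow-up needs repeated missed visits and failed contact efforts, so one missed call need not count.

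Most of this stands. A reader might infer that the plan definitely overwrites week-26 values; the documents support only that one literal reading does so. The ambiguity remains, however. Consent withdrawal has no threshold of repeated missed visits. SAP section 3 also shows that the sponsor saw the distinction: the imputation-based sensitivity analyses were reworded to refer to subjects without a week-26 measurement rather than to trial withdrawals in general. The responder text was edited too, but only for missing HbA1c, and its withdrawal clause stayed open-ended.

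Two further inferences are tempting and fail:

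- **That the clause is redundant beside the missing-value rule and can be deleted.** Visit reallocation shows otherwise: deletion could let early withdrawals count as responders on an early sample.
- **That the on treatment analysis contradicts itself.** SAP section 2 states that "The on treatment observation period includes data collected up to and including 7 days after treatment discontinuation", yet a subject who stops product a few days before Visit 40 is a non-responder. The window decides which data belong to the period; it does not promise that someone who stopped early may count as a success. Scoring premature discontinuation as failure is an explicit composite choice, consistent with a secondary estimand that supposes treatment continues to week 26.

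**Conclusion.** The concern holds as a wording defect with a small possible effect. The withdrawal clause in both responder endpoints is open-ended. Its literal application can turn a measured Visit 40 HbA1c below 7.5% into a failure in both analyses, against the week-26 definition and the rule on observed values.

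The likely size is about 0.2 to 0.4 percentage points on the responder percentage. This rests on withdrawal at the 5% ceiling, even timing, and responder rates of 30% to 60% that are not in the documents. Fewer withdrawals make it smaller. The 1.5 to 3.0 point bound needs every withdrawal to fall after Visit 40, which nothing in the documents suggests. A reader might also infer a biased treatment comparison; that would need such losses to differ between arms, and the documents give no ground to expect it.

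The endpoints are supportive, outside the three-step hierarchy, and not among the key supportive endpoints marked for disclosure in Protocol 4.2.2. The primary analysis and all confirmatory conclusions are unaffected.

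**What to change.** In SAP 2.4.1.1, for both responder endpoints:

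- **In trial analysis:** restrict the withdrawal clause by adding 'before the week-26 (Visit 40) HbA1c assessment'.
- **On treatment analysis:** add the same restriction to the withdrawal part of the clause. Leave the part on premature product discontinuation as it is.
- **Both analyses:** add one sentence saying that a subject with an HbA1c measured at the scheduled Visit 40 who withdraws or is lost only afterwards is not a non-responder on that ground and is scored on that value. The endpoint's other rules still apply.
- **Keep** the withdrawal clause itself, so that early withdrawals with a reallocated Visit 40A value remain non-responders, and keep the missing-HbA1c rule.

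Record the clarification in SAP section 3. The cost is a few words before database lock, plus a comparison of withdrawal date with Visit 40 sample date in the program. No new data are needed, and sample size and power do not change.
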